| 9.3 | Compliance with Trial Registration and Results Posting Requirements | 52 |

| | | |
|------|--|-----|
| 9.4 | Quality Management System..... | 52 |
| 9.5 | Data Management..... | 52 |
| 10.0 | LIST OF REFERENCES..... | 543 |
| 11.0 | APPENDICES..... | 58 |
| 11.1 | ECOG Performance Status..... | 58 |
| 11.2 | Common Terminology Criteria for Adverse Events V4.0 (CTCAE)..... | 58 |

TRIAL SUMMARY

[figure not shown]
| | |
|---------------------------------------|---|
| Title | A Phase II study of Pembrolizumab as Post-remission Treatment of Patients ≥ 60 with AML Who Are Not Transplantation Candidates |
| Short Title | Pembrolizumab as Maintenance Therapy for AML in CR1 |
| Protocol Number | |
| Phase | Phase II |
| Methodology | Open label |
| Study Center(s) | Single-center |
| Primary Objective | To evaluate the time to relapse (TTR) in patients > 60 years with AML in complete remission undergoing post-remission therapy with pembrolizumab. |
| Number of Subjects | 40 subjects |
| Diagnosis and Main Inclusion Criteria | Patients with AML in first complete remission/complete remission with incomplete count recovery who are not unable or unwilling to undergo allogeneic stem cell transplant or who allogeneic stem cell transplant is not indicated. |
| Study Product, Dose, Route, Regimen | Pembrolizumab, intravenous, 200mg, every 3 weeks with dosing adjustments as needed for toxicity |
| Duration of administration | Total duration of pembrolizumab is up to 2 years if patients tolerate the therapy and remain in complete remission |
| Reference therapy | Patients who achieve a complete response to induction chemotherapy followed by chemotherapy consolidation therapy who do not undergo allogeneic transplant are observed. Despite the high relapse rates in this group, there is not therapy that has been proven to be effective to prevent relapse. |
| Statistical Methodology | The relapse function will be estimated by using the Kaplan-Meier method. A 26% two-year TTR under the standard induction therapy is associated with a median of 12.3 months. The null hypothesis that the treatment with pembrolizumab offers no increase in TTR will be tested by determining if 12.3 months is within an 80% confidence interval around the median, a one-sided $\alpha=0.10$ test. |
| Estimated Enrollment Period | 18-24 months |
| Estimated duration of trial | 4 years, but with planned analysis at 18 months after last patient enrolled |

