1.2 Trial Diagram

2.0 OBJECTIVE(S) & HYPOTHESIS(ES)

2.1 Primary Objective(s) & Hypothesis(es)

- (1) **Efficacy Objective:** To evaluate the time to relapse in patients > 60 years with AML in complete remission undergoing post-remission therapy with pembrolizumab

Hypothesis: Post-remission treatment with pembrolizumab will improve time to relapse compared to historical controls in patients > 60 years with AML who are not candidates for HCT.

- (2) **Safety Objective:** To evaluate the safety and tolerability of pembrolizumab in patients > 60 years with AML

Hypothesis: Post-remission treatment with pembrolizumab will be safe and tolerable in patients \geq 60 years with AML who are not transplantation candidates

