3.2 Rationale

3.2.1 Rationale for the Trial and Selected Subject Population

Acute myeloid leukemia (AML) is a malignant hematopoietic disorder characterized by the unregulated growth of myeloid precursors (blasts) and associated marked reduction in normal hematopoiesis. It is the most common acute leukemia in adults, with an estimated 18,860 new cases of AML diagnosed per year in the United State and 10,460 deaths. [23] Disease related morbidity and mortality arise from cytopenias, leading to complications such as bleeding and/or infection, as well as end organ damage from the circulating blasts. If left untreated, AML can lead to death within weeks. [24]

The standard treatment for newly diagnosed AML consists primarily of an anthracycline combined with a nucleoside analogue, cytarabine. The goal of remission induction chemotherapy is the rapid restoration of normal bone marrow function. [25] Once a complete remission is attained, relapse invariably occurs without additional consolidation therapy. Consolidation approaches are based on prognosis and age, but may include 1-4 cycles of high dose cytarabine chemotherapy or allogeneic stem cell transplant. While consolidation therapy reduces relapse, up to 50% of younger patients still relapse. [26]

Although standard therapeutic approaches are tailored to younger patients, the median age of diagnosis of acute myelogenous leukemia (AML) is 67 years. [27] Unfortunately, the outcomes for patients older than 60 years are quite poor. Population studies in AML report 5-year survival rates of 3% to 8% compared to up to 50% for younger patients. [28] Intensive induction therapy, as described above, remains the standard of care for those elderly patients who are able to tolerate it, but rates of complete remission (CR) range from 20% to 60% dependent on the number of adverse prognostic conditions present. [29] The 2-year DFS of patients ≥ 60 yrs of age with AML who undergo induction therapy has been consistently at 24-26% in two large studies conducted in 2001 and 2010. [30; 31] Unfortunately, there have been no important advances in induction therapy since then.

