3.2.3 Rationale for Endpoints

3.2.3.1 Efficacy Endpoints

3.2.3.1.1 Primary Endpoint: Time to relapse (TTR)

The primary endpoint for this study is time to relapse (TTR). Patients with AML ≥ 60 years old in CR have a high relapse rate, which is the primary cause of death. The goal of PD-1 inhibition in AML is to harness the patient's immune system to eradicate submicroscopic disease and prevent relapse. As such, TTR was selected as the primary efficacy endpoint. TTR has been used as the endpoint in many similar clinical trials, and using this endpoint allow for valid comparison to historical controls. TTR is defined as survival in the absence of relapse, as defined by the Cheson criteria (see Section 12.3).

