7.2 Statistical Analysis Plan Summary

7.2.1 Primary Efficacy Objective: *To evaluate the time to relapse (TTR) in patients > 60 years with AML in complete remission undergoing post-remission therapy with pembrolizumab.* The time to relapse function will be estimated by the product-limit (Kaplan-Meier) method, with an appropriate 80% confidence interval. Death is considered a censoring event in determining TTR.

The median TTR will also be estimated, along with an appropriate confidence interval. Assuming an exponential time to failure distribution, 26% two-year TTR under the standard induction therapy is associated with a median of 12.3 months. The null hypothesis that the treatment with pembrolizumab offers no increase in TTR will be tested by determining if 12.3 months is within an 80% confidence interval around the median, a one-sided $\alpha=0.10$ test. The sensitivity of the treatment of death as a censoring event will be assessed by repeating the above analysis on relapse-free survival, where death and relapse are both considered events. Patients who drop out of the study will be treated as censored at the last observation time.

Potential prognostic factors for TTR in this population will also be explored. These include the use of consolidation therapy (0 vs 1-4), cytogenetic risk category (high-risk, intermediate risk, or low risk), FLT3 status (FLT3-ITD mutation present or absent), NPM1 status (NPM1 mutation present or absent), age >70 years, minimal residual disease, and ECOG performance status. The survival distributions for TTR will be computed using the Kaplan-Meier method and the log-rank test used to test for statistical differences in the distributions for the aforementioned exposure groups. Multivariate analysis using Cox regression will then be used to adjust for all significant covariates. Patients who drop out of the study will be treated as censored at the last observation time. Patients with missing covariate data will be excluded from this exploratory analysis.

7.2.2 Primary Safety Objective: *To evaluate the safety and tolerability of pembrolizumab in patients > 60 years with AML.* The NCI CTCAE type and grade of adverse events and their association with treatment will be tabulated. Section 8.3 contains a stopping rule for excess toxicity.

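### The 12.3-month null rests on a 2-year DFS figure but is tested on time to relapse with deaths censored, which shifts the primary test towards the drug if patients die in remission

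*Combined protocol and SAP*

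**What the plan says.** Section 3.2.1 gives the historical outcome as DFS: "The 2-year DFS of patients ≥ 60 yrs of age with AML who undergo induction therapy has been consistently at 24-26" per cent, from two large studies.

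Section 7.2.1 uses the upper figure under another name: "26% two-year TTR under the standard induction therapy is associated with a median of 12.3 months". The Trial Summary repeats the label. The null of no improvement is tested by asking whether 12.3 months lies inside an 80% confidence interval for the median TTR, described as a one-sided test at 0.10. For that curve, "Death is considered a censoring event in determining TTR". Section 7.2.1 adds: "The sensitivity of the treatment of death as a censoring event will be assessed by repeating the above analysis on relapse-free survival", with relapse and death both counted as events.

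Section 3.2.3.1.1 justifies the endpoint by stating that "using this endpoint allow for valid comparison to historical controls", but defines it differently: "TTR is defined as survival in the absence of relapse". The primary hypothesis in Section 2.1 is also historical: "Post-remission treatment with pembrolizumab will improve time to relapse compared to historical controls". Section 7.4 states 80% power at a true median TTR of 19.5 months.

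**The concern.** In a single-arm trial the benchmark stands in for the control group, so it must measure the same thing as the endpoint. The documents do not define DFS, but in its ordinary meaning a death in remission is an event. The tested TTR removes such deaths from the event count. A TTR curve therefore lies on or above the DFS curve for the same patients, even when the drug does nothing, and its median is compared with a null set by the lower curve.

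The definition of TTR in Section 3.2.3.1.1 reads as though deaths count, which contradicts the censoring rule in Section 7.2.1. No relapse-only historical figure is given from which a 2-year TTR or its median could be derived. The relapse rate of up to 80% in Section 3.2.1 carries no time point. At stake is the trial's one formal efficacy conclusion.

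**Working it through.** **Inputs from the documents.** 26% at 2 years and an exponential distribution (7.2.1); 24-26% as 2-year DFS (3.2.1); 40 patients and analysis 18 months after the last patient starts (1.1); accrual over 18-24 months (Trial Summary); alternative median 19.5 months (7.4).

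**Assumption.** f is the share of first events (relapse or death in remission) that are deaths. The documents do not give it, so a range is shown.

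**The plan's own figure.** 24 × ln 2 / (−ln 0.26) = 12.35 months, which reproduces the stated 12.3. The arithmetic is sound; the label is not. The low end of the DFS range, 24%, gives 24 × ln 2 / (−ln 0.24) = 11.66 months.

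**Matching TTR null.** With constant hazards, the relapse hazard is (1−f) times the DFS hazard, so the median TTR of an ineffective drug is 12.35/(1−f): 13.0 months at f=5%, 13.7 at 10% and 15.4 at 20%.

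**False-positive rate of the planned test.** Simulation: 40,000 trials per cell, n=40, uniform 24-month accrual plus 18 months, exponential cause-specific hazards, no other dropout. The test rejects if the lower 80% limit for the Kaplan-Meier median exceeds 12.3. The plan names no interval method, so three are shown. There is no drug effect.

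| True 2-year DFS | f | Plain | Log | Log-log |
|---|---|---|---|---|
| 26% | 0 | 0.136 | 0.136 | 0.079 |
| 26% | 5% | 0.161 | 0.181 | 0.128 |
| 26% | 10% | 0.208 | 0.236 | 0.181 |
| 26% | 20% | 0.364 | 0.401 | 0.328 |
| 24% | 0 | 0.090 | 0.090 | 0.049 |
| 24% | 10% | 0.154 | 0.177 | 0.132 |
| 24% | 20% | 0.286 | 0.321 | 0.254 |

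The spread at f=0 comes from the interval method, not the mismatch. Subtracting the f=0 row at DFS 26%, the mismatch itself adds about 2.5-5 percentage points at f=5%, 7-10 at 10% and 23-27 at 20%. Accrual over 18 months changes little (f=10%: 0.214/0.241/0.186).

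**RFS against 12.3, DFS 26%.** For f from 0 to 30%, rejection stays at 0.131-0.136 (plain and log) and 0.075-0.079 (log-log).

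**Offset from choosing 26%.** If true DFS is 24%, the TTR null median passes 12.3 only when f exceeds 1 − 11.66/12.3 = 5.2%.

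**The case against.** Four points deserve weight.

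1. **RFS is already planned.** Repeating the same analysis on RFS includes the test against 12.3, and that is the like-for-like comparison. No section gives a go/no-go rule or says what follows if TTR and RFS disagree. This softens the problem, because a reader will see both results. But the null hypothesis is stated on TTR and RFS is called a sensitivity analysis, so the formal conclusion follows the mismatched test.

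2. **The link to DFS is inferred.** Section 7.2.1 cites no source for 26%. That is true, but no other figure in the documents fits. If a relapse-only source exists, the plan needs to cite it.

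3. **The size depends on assumptions.** f is unknown, and 12.3/(1−f) needs proportional, constant hazards. Holding 26% at 24 months and using a Weibull shape of 0.7 (an assumption), the null TTR median at f=10% is only 10.8 months and rejection is 0.048/0.059/0.039 (plain/log/log-log). With shape 1.3, rejection is already 0.41/0.41/0.29 at f=0, for TTR and RFS alike. So the exponential conversion can outweigh the mismatch, and the tabulated rates are not a forecast of the trial's error rate. At every shape examined, however, the mismatch raised TTR rejection above RFS whenever f>0.

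4. **TTR has a rationale.** The drug is meant to prevent relapse, and RFS costs power. That is a fair reason to keep TTR, but with a null that matches it.

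**Conclusion.** The point holds and should be corrected before the primary test is relied on. The documents support 26% only as DFS, yet it is labelled TTR and tested with deaths censored. The direction is clear: relative to a matched comparison, any deaths in remission favour the drug. A net excess over the nominal 0.10 also depends on f, the true DFS within 24-26%, the hazard shape and the interval method. Under the plan's exponential model with DFS at 26%, the false-positive rate is 0.18-0.24 at f=10% and 0.33-0.40 at f=20%. With DFS at 24% it is 0.13-0.18 and 0.25-0.32. If f is zero there is no bias, but the label and the two conflicting definitions of TTR still need correcting.

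**What to change.** Choose one of two routes.

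- **Option 1:** make RFS (relapse or death) the endpoint formally tested against 12.3 months, with death-censored TTR or cumulative incidence of relapse as supportive.
- **Option 2:** keep TTR primary and derive its null from relapse-only data in the same historical cohorts.

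Either way, relabel the 26% as 2-year DFS in the Trial Summary and Section 7.2.1, reconcile Section 3.2.3.1.1 with Section 7.2.1, name the confidence-interval method and restate the power in Section 7.4.

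Neither route needs new patients or trial data. Option 1 changes the Trial Summary and Sections 2.1, 3.2.3.1.1, 7.2.1 and 7.4, and it costs power. Suppose the drug acts on relapse only, with hazard ratio 12.3/19.5 = 0.63. The RFS median is then 12.3/(0.9 × 0.631 + 0.1) = 18.4 months at f=10% and 12.3/(0.8 × 0.631 + 0.2) = 17.5 at f=20%. RFS power is 0.60-0.71 and 0.51-0.63 respectively, against 0.67-0.78 at f=0 under the same rule.

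Option 2 needs a historical figure that the documents do not contain. Against a null of 12.3/(1−f), its power at the same hazard ratio is 0.69-0.75 at f=10% and 0.67-0.74 at f=20%. If the true median TTR is the stated 19.5 months, power is only 0.54-0.61 and 0.35-0.42.

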1.0 TRIAL DESIGN

1.1 Trial Design

This is a phase II, single-center, single-arm trial to evaluate the efficacy and safety of pembrolizumab in post-remission treatment of patients ≥ 60 years with AML who are not candidates for HCT. Patients must have achieved CR or CRi with induction chemotherapy and have an ECOG performance status of 0-1. Patients can receive no consolidation or up to 4 cycles of consolidation per treating physicians' preference. Patients are eligible if their last dose of chemotherapy was received within 3 months of trial enrollment. Remaining in CR or CRi is required prior to enrollment. The enrollment target for this study is 40 patients evaluable for efficacy. Planned analysis will occur 18 months after the initiation of treatment of the last patient on the trial.

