7.0 STATISTICAL ANALYSIS PLAN

7.1 Analysis Samples

For both the primary safety and efficacy endpoints, the analysis sample will be eligible patients who have taken at least one dose of pembrolizumab. Patients who are eligible but withdraw prior to taking the first dose will not be included in these analyses and will be replaced, so that, barring early stopping, the analysis sample will be 40 patients who have taken at least one dose of drug.

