7.2.3 Secondary Efficacy Objective: *To evaluate overall survival with post-remission pembrolizumab treatment in patients \geq 60 years with AML.* The analysis plan is similar to that of TTR. Assuming an 8% five-year survival rate with induction therapy alone, median overall survival is 17.2 months.

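### If the interval for the median is Kaplan-Meier based, the primary test ignores relapses after 12.3 months; a one-sample log-rank test on the plan's own null curve would gain about 6 to 19 points of power

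*Combined protocol and SAP*

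**What the plan says.** Section 7.2.1 estimates the TTR function by Kaplan-Meier. The median is to be given with a suitable confidence interval, and no method is named for it. The null hypothesis is "tested by determining if 12.3 months is within an 80% confidence interval around the median", described as a one-sided test at 0.10. The Trial Summary repeats this rule. No other primary test is planned; the log-rank test and Cox model in 7.2.1 serve only the exploratory prognostic factors.

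The null value has this source: "Assuming an exponential time to failure distribution, 26% two-year TTR under the standard induction therapy is associated with a median of 12.3 months". Deaths and dropouts are censored. Section 7.4 states 80% power if the true median is 19.5 months or more.

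On size and timing, section 7.1 says "the analysis sample will be 40 patients who have taken at least one dose of drug". The Trial Summary expects 18-24 months of enrolment, and section 1.1 says "Planned analysis will occur 18 months after the initiation of treatment of the last patient on the trial". For overall survival, section 7.2.3 says "The analysis plan is similar to that of TTR", so the same test form carries over.

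**The concern.** At the planned analysis each patient has at least 18 months of potential follow-up, and the earliest enrolled have 36-42 months. Asking whether a Kaplan-Meier interval for the median contains 12.3 months amounts to testing S(12.3) = 0.5. Without censoring before 12.3 months, it is a count of patients still relapse-free at that time. With early censoring it is the Kaplan-Meier estimate at 12.3 months. Either way, nothing after 12.3 months can change the decision.

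The plan obtains 12.3 months from a fully specified exponential curve, so a test that uses all follow-up needs no assumption that the plan does not already make. At stake is the chance that a 40-patient single-arm trial misses a real effect of the size it was designed to detect.

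**Working it through.** **Inputs from the documents.** N = 40; null median 12.3 months, exponential (24 × ln 2 / −ln 0.26 = 12.35); alternative median 19.5 months; one-sided 0.10; accrual 18-24 months (taken as uniform); analysis 18 months after the last patient starts. The documents give no death or dropout rate, so the base case has none.

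**1. Reproducing the stated 80%.** Under the alternative, S(12.3) = exp(−ln 2 × 12.3/19.5) = 0.646. With no censoring before 12.3 months, the Kaplan-Meier test is a binomial rule on 40 patients. With 24 of 40 relapse-free, the linear statistic is (0.60 − 0.50)/√(0.60 × 0.40/40) = 1.29, just above 1.28, so the linear interval rejects. The log-log interval first rejects at 25.

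| Rule | Interval | True one-sided error | Power at 19.5 months |
|---|---|---|---|
| ≥ 24 of 40 | linear, log | 0.134 | 0.782 |
| ≥ 25 of 40 | log-log, arcsine | 0.077 | 0.675 |

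The linear reading is within two points of the stated 80%, but its error exceeds 0.10. The rule that respects 0.10 reaches 80% power only at a median of about 21.6 months.

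**2. Relapses that cannot count.** With λ = ln 2/19.5 = 0.03555 and accrual A, expected relapses by the analysis are 40 × [1 − (e^(−18λ) − e^(−(18+A)λ))/(Aλ)].
- A = 18: 40 × (1 − 0.2493/0.6398) = 24.4.
- A = 24: 40 × (1 − 0.3027/0.8531) = 25.8.
- By 12.3 months: 40 × (1 − 0.646) = 14.2.

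The unused share is 1 − 14.2/24.4 = 42% to 1 − 14.2/25.8 = 45%. If follow-up stops at 24 months per patient, expected relapses are 22.3-22.5 and the share is about 37%.

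**3. One-sample log-rank test.** Compare observed relapses O with E = Σ (ln 2/12.3) × follow-up time, and reject if (O − E)/√E < −1.28. Under the alternative with A = 18, O averages 24.4 and E averages 24.4 × 19.5/12.3 = 38.7, so the statistic centres near (24.4 − 38.7)/√38.7 = −2.3. By simulation (40,000-60,000 trials per scenario):
- full follow-up: power 0.86-0.87, error 0.09;
- follow-up capped at 24 months: power 0.84-0.85, error 0.09.

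**4. Size of the gain.** The smallest gain is 0.84 − 0.78 = 6 points (24-month cap, linear interval). The largest is 0.87 − 0.68 = 19 points (full follow-up, log-log interval). These ends compare tests of different true error. At an equal error of 0.10, a randomised binomial rule puts weight (0.1000 − 0.0769)/(0.1341 − 0.0769) = 0.404 on 24 of 40, giving 0.675 + 0.404 × (0.782 − 0.675) = 0.718. The log-rank test calibrated to 0.10 has 0.88-0.89 with full follow-up, a gain of about 16-17 points.

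With an assumed 10-20% a year of death or dropout and full follow-up, the log-rank test has 0.80-0.85 and the Kaplan-Meier interval 0.66-0.75, a gain of 7-16 points.

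**5. Shape of the null curve.** Weibull nulls, 24-month accrual, full follow-up, false-positive rates:

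| Held fixed | Shape | One-sample log-rank | Kaplan-Meier interval |
|---|---|---|---|
| 26% at 24 months | 0.7 | 0.06 | 0.01-0.02 |
| 26% at 24 months | 1.3 | 0.13 | 0.29-0.41 |
| median 12.3 months | 0.7 | 0.31 | 0.08-0.13 |
| median 12.3 months | 1.3 | 0.01 | 0.08-0.13 |

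**The case against.** The strongest objection is that the power loss rests on a reading. Kaplan-Meier is named for the TTR function, not for the interval around the median, and the exponential assumption appears in the very next sentence. An exponential-model interval uses every relapse and has power 0.86-0.87 on the log scale, or 0.81-0.83 in linear Wald form. The stated 80% does not settle the matter, because both families contain variants near it. This stands: the loss is conditional, and the unnamed method is itself a gap.

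Second, follow-up may be shorter than the calendar allows. The Trial Summary gives participation as two years per patient, whereas section 6.1.5.4 follows disease status for up to five years from enrolment. Later relapses may also be found less promptly, since monitoring off treatment is a blood count every 12 weeks. This stands, and sets the lower end of the gain.

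Third, a reader might infer that the log-rank test is simply the more robust choice. The documents do not support that. It is less shape-sensitive if the two-year rate is the fixed point, which is the figure the plan starts from. It is more so if the 12.3-month median is the fixed point, which is the value the plan tests. It also needs the null curve beyond 24 months, for which the documents give no data.

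Fourth, the benchmark may not fit the endpoint. Section 3.2.1 reports 24-26% as two-year disease-free survival, while TTR censors deaths. If the true TTR hazard without any drug effect were 0.75-0.85 of the benchmark (an assumption), the log-rank test would reject 33-60% of the time and the Kaplan-Meier intervals 23-54%. Both tests share this problem, and the more powerful test does not cure it.

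**Conclusion.** This is an inexpensive improvement, not a mistake in the plan. Testing a median through its interval is a legitimate phase II method. A reader might infer that the primary test is invalid or that the 80% power claim is wrong. The documents support neither: the linear Kaplan-Meier reading gives 78%, and the interval method is open. Nor are the later relapses lost to the trial, since they still inform the Kaplan-Meier curve and the exploratory analyses.

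On the Kaplan-Meier reading, a one-sample log-rank test raises power at 19.5 months from 0.68-0.78 to 0.84-0.87. The chance of missing that effect falls from 22-32% to 13-16%. These figures assume exponential relapse times, uniform accrual, no early death or dropout, and a null curve that is correct for the endpoint. With the assumed death or dropout, both tests lose power but a gain of 7-16 points remains.

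**What to change.** 1. Match the benchmark to the endpoint first. Either apply the 26% two-year figure to relapse-free survival, or justify a separate benchmark for TTR with deaths censored.
2. In section 7.2.1 and the Trial Summary, make the primary test a one-sided 0.10 one-sample log-rank test: O against E = Σ (ln 2/12.3) × follow-up time, rejecting if (O − E)/√E < −1.28. If step 1 changes the null median, use that value in E.
3. Keep the Kaplan-Meier curve and the median with its 80% interval as estimates, and name the interval method. Keep the interval test as a sensitivity analysis.
4. State the follow-up that enters the test (up to 24 months per patient, or all available), and restate the power in section 7.4 for the new test.
5. Say whether overall survival in section 7.2.3 uses the same form against its own benchmark.

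The cost is SAP wording and a new power calculation, with no added patients, visits or data. The downside is reliance on the whole exponential null curve, including beyond 24 months. The sensitivity analysis in step 3 partly guards against this.

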4.1.3 Subject Exclusion Criteria

The subject must be excluded from participating in the trial if the subject:

- Has a diagnosis of Acute Promyelocytic Leukemia (APL) as defined by the World Health Organization. [59]

2. Eligible and willing to proceed with an allogeneic stem cell transplant with an acceptable stem cell donor
3. Has favorable risk AML as defined by the presence of isolated t(8;21) or inv(16) or t(16;16)(p13.1;q22) on a standard karyotype or mutated NPM1 with concurrent wild-type FLT3 on molecular testing.
4. Is currently participating in or has participated in a study of an investigational agent or using an investigational device within 4 weeks of the first dose of treatment.
5. Has a diagnosis of immunodeficiency or is receiving systemic steroid therapy or any other form of immunosuppressive therapy within 7 days prior to the first dose of trial treatment.
6. Has had a prior monoclonal antibody within 4 weeks prior to study Day 1 or who has not recovered (i.e., \leq Grade 1 or at baseline) from adverse events due to agents administered more than 4 weeks earlier.
7. Has had prior chemotherapy, targeted small molecule therapy, or radiation therapy within 2 weeks prior to study Day 1 or who has not recovered (i.e., \leq Grade 1 or at baseline) from adverse events due to a previously administered agent.
 - Note: Subjects with \leq Grade 2 neuropathy are an exception to this criterion and qualify for the study.
 - Note: If subject received major surgery, they must have recovered adequately from the toxicity and/or complications from the intervention prior to starting therapy.
8. Has a known additional malignancy that is progressing or requires active treatment. Exceptions include basal cell carcinoma of the skin, squamous cell carcinoma of the skin, or in situ cervical cancer that has undergone potentially curative therapy.
9. Has known active central nervous system (CNS) involvement. Subjects with previously treated CNS disease may participate provided they are stable (without evidence of CNS leukemia at the time of screening and any neurologic symptoms have returned to baseline) and are not using steroids for at least 7 days prior to trial treatment.

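### Exclusion criterion 3 makes every eligible NPM1-mutated patient FLT3-mutated, so the stand-alone NPM1 log-rank test in 7.2.1 cannot separate NPM1 from FLT3

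*Combined protocol and SAP*

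**What the plan says.** Section 4.1.3, criterion 3, excludes favourable-risk AML. Its molecular part covers "mutated NPM1 with concurrent wild-type FLT3 on molecular testing". Section 7.1 then restricts the data: "the analysis sample will be eligible patients who have taken at least one dose of pembrolizumab". The planned number is 40.

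Section 7.2.1 introduces an exploratory analysis: "Potential prognostic factors for TTR in this population will also be explored". Among seven listed factors are "FLT3 status (FLT3-ITD mutation present or absent") and "NPM1 status (NPM1 mutation present or absent"). Each factor is tested singly, with "the log-rank test used to test for statistical differences in the distributions for the aforementioned exposure groups". After that, "Multivariate analysis using Cox regression will then be used to adjust for all significant covariates". Patients with missing covariates are dropped from this analysis. No significance level, power or decision rule is given for it, and the NPM1 comparison is neither stratified by FLT3 nor restricted to a FLT3 group.

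**The concern.** Of the four NPM1-by-FLT3 combinations, the eligibility rule removes one. The NPM1-mutated group is then entirely FLT3-mutated, while the NPM1-negative group may hold both FLT3 types. That is confounding by design and not chance imbalance, so a larger sample would not remove it. Nothing in 7.2.1 acknowledges it.

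Two errors can follow. If FLT3 mutation shortens time to relapse and NPM1 does nothing, NPM1 can look adverse. If NPM1 is favourable within FLT3-mutated patients, the two effects can cancel and NPM1 can look inert. Because the single-factor results decide what enters the Cox model, either error also affects covariate selection.

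At stake is a secondary statement about prognosis in the trial report, not the conclusion about pembrolizumab.

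**Working it through.** The plan states no figure for this analysis, so there is none to reproduce.

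**Step 1. Cells left after exclusion 3**

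| | FLT3 wild-type | FLT3-mutated |
|---|---|---|
| NPM1-mutated | empty by eligibility | possible |
| NPM1-negative | possible | possible |

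Dropping patients with missing covariates does not refill the empty cell.

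**Step 2. What the NPM1 test estimates.** Let q be the FLT3-mutated share of NPM1-negative patients. To first order:

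log(apparent NPM1 HR) = log(NPM1 HR within FLT3-mutated) + (1 − q) × log(FLT3 HR)

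The documents give no prevalences or hazard ratios (HR). Two assumed settings for N = 40:
- A: 10 FLT3-mutated, 5 of them NPM1-mutated, so q = 5/35 = 0.143.
- B: 12 FLT3-mutated, 7 of them NPM1-mutated, so q = 5/33 = 0.152.

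With no NPM1 effect, the apparent NPM1 HR is:
- FLT3 HR 1.5: 1.5^0.857 = 1.42 (A), 1.5^0.848 = 1.41 (B)
- FLT3 HR 2: 1.81 (A), 1.80 (B)
- FLT3 HR 3: 2.56 (A), 2.54 (B)
- FLT3 HR 1: 1.00, no bias

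With a true NPM1 HR of 0.5 and FLT3 HR 2: 0.5 × 1.81 = 0.91 (A), 0.5 × 1.80 = 0.90 (B). A halved hazard shows as almost nothing.

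**Step 3. How often the tests reject.** Simulation of settings A and B with exponential relapse times and a base median of 12.3 months (the null median in 7.2.1). Follow-up is 18–42 months: analysis 18 months after the last patient starts (1.1), plus the 24-month upper end of accrual in the Trial Summary. Tests are two-sided at 5%, an assumed level. The two-step plan is reduced to NPM1 and FLT3. NPM1 counts as a final positive if it passes the screen and either FLT3 does not, or NPM1 stays significant in a Cox model with both.

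| True effects | NPM1 log-rank significant | NPM1 significant after Cox step |
|---|---|---|
| FLT3 HR 1, NPM1 HR 1 | about 6–7% | not needed |
| FLT3 HR 1.5, NPM1 HR 1 | about 16–17% | about 5–9% |
| FLT3 HR 2, NPM1 HR 1 | 28–32% | about 5–9% |
| FLT3 HR 3, NPM1 HR 1 | 52–61% | about 5–9% |

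The last column assumes that every FLT3 mutation is ITD, and its range covers all three FLT3 hazard ratios. If two of the seven NPM1-mutated patients in setting B carry a non-ITD FLT3 mutation, and so are coded FLT3-ITD absent, the final rate at FLT3 HR 2 is about 14%.

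**Step 4. Masking.** With NPM1 HR 0.5 and FLT3 HR 2, the planned NPM1 log-rank rejects in about 5–7% of trials. The same test within FLT3-mutated patients rejects in 18–22%. A factor lost at the screen never reaches the Cox model.

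**Step 5. Other inputs.** With 4 or 6 NPM1-mutated patients, 2–11 FLT3-mutated among the NPM1-negative and a 15-month base median, the log-rank false-positive rate is 13–18% at FLT3 HR 1.5 and 21–33% at HR 2. Within FLT3-mutated patients the HR 2 rate falls to 7–13%. The excess over 5% there is small-sample error.

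**Step 6. Power of the clean comparison.** Schoenfeld, true HR 2: power = Φ(√(d·p·(1 − p)) × ln 2 − 1.96), with d events and p the share NPM1-mutated.
- d = 8, p = 4/9: Φ(0.974 − 1.96) = 0.16
- d = 13, p = 6/16: Φ(1.210 − 1.96) = 0.23

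**The case against.** A reader might infer that the plan will report FLT3's effect as NPM1's whatever NPM1 really does. The documents do not support that. The contrast is a mixture. It equals FLT3's effect alone only if NPM1 has none within FLT3-mutated patients and no NPM1-negative patient is FLT3-mutated. The effects can cancel, and if FLT3 has no effect there is no such bias.

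A reader might also take 28–61% as the plan's error rate. It describes an intermediate screen. FLT3 is a listed factor, and when it drives relapse it usually passes the same screen: in about 80% of the trials with a significant NPM1 test at FLT3 HR 2, and about 96% at HR 3. The Cox model can then separate the two, provided some NPM1-negative, FLT3-mutated patients enrol. This stands, and it brings the final false-positive rate close to nominal. It does not cover trials in which NPM1 passes the screen and FLT3 does not, and it does nothing for masking.

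The ITD mismatch is a question of wording. Criterion 3 speaks of wild-type FLT3 and the covariate of ITD only. If wild-type was meant as ITD-negative, the two agree and the 5–9% applies. The documents do not say. On either reading the NPM1-mutated, FLT3 wild-type cell is empty.

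Finally, the analysis is exploratory, with no alpha or decision rule, and every prevalence and hazard ratio above is assumed. Both are true, and both limit the severity.

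**Conclusion.** Wrong as written, low severity. That the stand-alone NPM1 test is confounded by FLT3 follows from 4.1.3, 7.1 and 7.2.1 alone and needs no outside figure. Its size does. In the assumed settings the screen's false-positive rate runs from about 16–17% (FLT3 HR 1.5) to 52–61% (HR 3). After the planned Cox step it is about 5–9% if ITD captures all FLT3 mutations, or about 14% in the one non-ITD case examined. Loss of a real favourable NPM1 effect at the screen is not repaired. The simulations leave out the other five listed factors. The primary test of time to relapse does not use NPM1 or FLT3 and is unaffected, as are the overall survival and safety analyses. The eligibility rule itself is not in question.

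**What to change.** In 7.2.1, replace the stand-alone NPM1 test, and preferably the separate FLT3 factor too, with one three-level factor: FLT3 wild-type; FLT3-mutated and NPM1 wild-type; FLT3-mutated and NPM1-mutated. Alternatively, assess NPM1 only within FLT3-mutated patients. State which FLT3 mutations count, and use the same definition in 7.2.1 as in exclusion criterion 3. Report the NPM1 contrast descriptively, as an estimate with its interval and patient counts, and do not let a significance screen decide whether it is shown.

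The cost is mainly SAP wording. Applying criterion 3 calls for NPM1 and FLT3 results at entry, but the flow chart schedules only flow cytometry and cytogenetics on the marrow. The case report form should therefore be checked to confirm that both results, including any non-ITD FLT3 mutation, are recorded. The downside is that the NPM1 contrast will rest on few patients, with power of roughly 0.16–0.23 for a hazard ratio of 2, which is why it should be descriptive.
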